PRoFLUID statistical analysis plan

The PRoFLUID investigators

Finalized on 21-09-2025

Methods

Design

PRoFLUID is an international prospective observational cohort study in critically ill invasively ventilated patients that receive ventilation for at least 24 hours. We expect a minimum of 200 ICUs from 30 countries to participate in this study. Patients in participating centers are screened on a daily basis. Eligible patients are included during a 28-day period, from Monday at 8:00 AM to the Monday 4 weeks later at 7:59 AM (in time zones of the participating centers).

Centers are expected to include 20 consecutive patients. After this, centers can either stop study inclusion or decide to enroll more patients. Centers that decide to continue enrollment will have to enroll the next 20 consecutive patients before they are given the option to stop study enrollment, until day 28.

Data regarding fluid administration, vasopressor use, diuretics use, oxygen exchange, and kidney function will be collected daily from the start of invasive ventilation. Collection will be retrospective, for the previous day. Clinical complications will be evaluated on day 90 after start of invasive ventilation, death or hospital discharge, whichever comes first.

Patients

Patients are eligible for participation in PRoFLUID if: (I) admitted to a participating ICU; (II) receiving invasive ventilation within three days of ICU admission; and (III) having received invasive ventilation for at least 24 hours. Patients younger than 16 years, and patients that are transferred under invasive ventilation from another ICU are excluded from participation in the study.

Primary outcome

The primary outcome is the provided fluid therapy in terms of volume per indication in the first 3 days after start of invasive mechanical ventilation, particularly the volumes of resuscitation fluid.

Secondary outcome

Secondary outcomes of this analysis consider the type of fluid used during the first 3 days after start of invasive mechanical; cumulative fluid balance over the first 7 days after start of invasive mechanical ventilation; the timing of start of diuretics or ultrafiltration . Additionally, secondary outcomes will include patient related outcomes such as mortality during ICU and hospital admission; ventilator free days at day 28; and duration of ventilation in survivors and non-survivors.

Stratification

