Outcomes will be analyzed across the entire cohort. Stratification will be performed over tertiles of total sequential organ failure score (SOFA) on day of intubation, specifically:

- Moderate: First tertile
- Severe: Second tertile
- Very severe: Third tertile

If SOFA components are missing at baseline, the missing values will be imputed by the mean of the patient's available component scores to calculate the total SOFA score. Patients without any data on baseline SOFA are excluded from the analysis.

Analysis plan

Descriptive statistics will be used to describe study population and fluid management parameters. Data are presented as numbers and percentages for categorical variables and as means (+/- SD) or median and interquartile range [IQR] according to distribution. Where appropriate, statistical uncertainty will be expressed by 95% confidence intervals.

We will describe the volume per indication for intravenous fluid therapy over the following indication categories:

- Resuscitation fluid
 - Prescribed in response to hemodynamic impairment or shock
 - Usually, isotonic crystalloids or colloids
 - At a rate of at least 166ml/h (1L/6 hours)
 - Usually much faster or as a bolus
- Maintenance or replacement fluid:

- Maintenance Fluids
 - Cover daily water and electrolyte needs
 - Up to 100 ml/h infusion rate.
- Replacement fluids
 - To address fluid losses
 - For example given for burns, dehydration, losses through drains, keto-acidosis
 - Can have faster (e.g. > 100ml/h) infusion rates
 - Are not given as bolus
- Unknown indication
 - Prescribed intravenous fluid therapy for which it is impossible to distinguish between resuscitation, maintenance or replacement

The volumes of intravenous fluid therapy per indication will also be examined in the context of all other fluids that are provided:

- Fluid as a carrier for intravenous medication
- Fluid to ensure catheter patency
- Cellular blood product transfusion
- Oral feeding
- Oral fluids
- Parenteral feeding

These volumes will be described as absolute mean volumes in mL with 95% confidence interval, as mean volumes per kilogram of body weight with 95% confidence interval, and relative to each other (as percentage of total).

Fluid volumes will be plotted using cumulative distribution plots that display fluid volumes over the first 3 days after intubation.

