To adjust for case-mix differences across SOFA tertiles and investigate factors that influence fluid management, multivariate regression analysis will be performed, adjusting the administered fluid volumes for the following baseline variables: duration of first study day; sex; age; weight; and admission diagnosis. The differences in fluid administration between SOFA tertiles be evaluated.

Secondary endpoints may be described and differences in the distributions between SOFA tertiles regions may be tested using regression analysis or Kruskal-Wallis test. Associations between fluid balance and clinical outcomes will be assessed using Cox proportional hazards modelling with fluid balance as a time-dependent covariate. The model will be adjusted for duration of day 0, age, sex, weight, baseline SOFA, and admission diagnosis. Other covariates may also be considered for the model if deemed appropriate.

Sensitivity testing will be performed to assess the robustness of findings. All statistical analyses will be performed using R. We consider $p < 0.05$ to be statistically significant.

Table 1 – Minimal list of proposed tables and figures

	Description
Main paper	
Table 1	Baseline Characteristics
Table 2	Clinical outcomes
	Cumulative distribution of volumes per indication for fluid administration over the first 3 days after intubation:
Figure 1	A four panels figure showing: A) Cumulative distribution of volume of resuscitation fluid per stratifying variable; B) Cumulative distribution of volume of maintenance or replacement fluid per stratifying variable C) Cumulative distribution of volume of IV medication per stratifying variable; and D) Cumulative distribution of volume of cellular blood product transfusion per stratifying variable
	Fluid input, output and balance over first 7 days after intubation
Figure 2	A three panels figure of line plots with 95% CI showing: A) total volume of fluid volume input per admission day by stratification variable; B) total volume of fluid volume output per admission day by stratification variable; C) Daily fluid balance by stratification variable.
	Types of fluid prescribed

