Figure 3	A two panels figure of stacked bar plots showing proportional fluid composition. Panel A reports the proportional distribution of major fluid categories Panel B details the composition of the 'other' fluid category by SOFA class, Proportions are expressed relative to the total volume of fluid administered within each SOFA class.
Online Supplement	
eTable 1	Steering committee
eTable 2	National coordinators
eTable 3	Participating centers
eTable 1	Proportion of missing data per variable
eTable 2	Mean volumes per indication for fluid administration per study day and stratification variable.
eTable 3	Mean volumes per type of fluid per study day and stratification variable.
eTable 4	Factors associated with fluid management
eTable 5	Results of multivariate regression for the association of fluid balance and mortality
eFigure 1	Participant flow diagram
eFigure 2	Cumulative distribution of volumes per indication for fluid administration for other indications
eFigure 3	Proportional volume of fluid type per day and stratification variable.
eFigure 4	Daily serum lactate, sodium and chloride.
eFigure 5	Daily SOFA over the three days after intubation Line plot reporting A) total SOFA, B) cardiovascular SOFA, C) respiratory SOFA, and D) renal SOFA according to randomization group. Mean and 95% confidence intervals will be reported.

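### Does leaving out patients with no baseline SOFA data contradict the aim of analysing the entire cohort?

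*SAP*

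**What the plan says.** Three parts of the SAP bear on this.

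- **Stratification.** The section begins "Outcomes will be analyzed across the entire cohort" and then introduces tertiles of total SOFA on the day of intubation. A patient with some components missing has them filled in with the mean of his or her recorded components. The section ends: "Patients without any data on baseline SOFA are excluded from the analysis".
- **Analysis plan.** Of the fluid volumes by indication, it says: "These volumes will be described as absolute mean volumes in mL with 95% confidence interval". That description needs no SOFA score. SOFA is needed for the regression comparing volumes between tertiles and for the Cox model, of which it says: "The model will be adjusted for duration of day 0, age, sex, weight, baseline SOFA, and admission diagnosis".
- **Design.** "Centers are expected to include 20 consecutive patients", and data on fluids, vasopressors, diuretics, "oxygen exchange, and kidney function will be collected daily from the start of invasive ventilation".

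Baseline SOFA is not among the eligibility criteria in the Patients section, so a patient without it is still an enrolled patient.

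**The concern.** The exclusion carries no limiting words, and nothing else in the SAP supplies them. If it covers every analysis, patients enrolled in a consecutive series drop out of the overall volumes, baseline characteristics and clinical outcomes for want of a variable that those results do not use. This would touch the primary outcome, which is fluid volume by indication.

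Two analysts could also follow the SAP in good faith and report different overall denominators. One would keep these patients in the overall column and leave them out of the tertile columns; the other would leave them out of both. If the excluded patients received unusually large or small volumes, the two overall means would differ.

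**Working it through.** **Step 1: set the two sentences side by side.** They contradict each other only if the entire cohort means every enrolled patient and, at the same time, the exclusion applies to every analysis. Two natural readings avoid this.

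- *Narrow.* The exclusion follows directly on the rule for computing total SOFA, under the heading Stratification. It then governs the stratified and SOFA-adjusted results, and the overall results keep everyone.
- *Broad.* The exclusion defines the analysis set. The entire cohort then means that set pooled, as opposed to the tertiles introduced in the next sentence. The three tertiles add up to the overall total.

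The wording does not settle which is meant, but each reading is consistent in itself.

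**Step 2: see which displays are affected.** Figures 1, 2 and 3, the two volume tables (eTables 2 and 3, for example "Mean volumes per indication for fluid administration per study day and stratification variable") and eFigure 3 refer to the stratifying variable or SOFA class. They need SOFA under either reading. Table 1, Table 2, the missing-data eTable 1, eTables 4 and 5, and eFigures 1, 2 and 4 name no stratum. A title that names none does not show that an unstratified display is planned. The list is described as minimal, and eFigure 2 ("Cumulative distribution of volumes per indication for fluid administration for other indications") is the companion of Figure 1, whose panels are all stratified.

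**Step 3: ask how many patients could be affected.** Only a patient with no recorded component at all is excluded. These are ICU patients ventilated for at least 24 hours, with vasopressor use, oxygen exchange and kidney function recorded daily. Those items bear on the cardiovascular, respiratory and renal components, which eFigure 5 plans to plot. A patient lacking all of them on the first day may well lack first-day fluid data too, and would then contribute little to the volumes under either reading.

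**Step 4: illustrate the size.** The SAP gives neither a sample size nor a share without SOFA. The figure of 4000 is 200 ICUs × 20 patients; 200 is a stated minimum and 20 an expectation, so 4000 is a working figure and not a target. The shares, the volume difference, the SD and the intracluster correlation are assumptions.

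- Shift in the overall mean = share excluded × difference in mean volume between excluded and retained patients.
- Half-width of the 95% confidence interval = 1.96 × SD / √4000. This is 46.5 mL for an SD of 1500 mL and 93.0 mL for 3000 mL, ignoring clustering.

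| Share without SOFA | Patients | Shift for a 500 to 1000 mL difference |
|---|---|---|
| 0.5% | 20 | 2.5 to 5 mL |
| 1% | 40 | 5 to 10 mL |
| 5% | 200 | 25 to 50 mL |

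Allowing for clustering by centre with an intracluster correlation of 0.05, the design effect is 1 + 19 × 0.05 = 1.95, and the half-widths become 64.9 to 129.8 mL. At 0.5% or 1% the shift is small against either set. At 5% it exceeds the half-width only with the largest difference, the smallest SD and clustering ignored (50 against 46.5 mL). A share that high would mean one patient in twenty with no SOFA component recorded.

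**The case for a change.** The strongest case for a change is that an analysis plan exists to fix denominators in advance. Here the denominator of the primary description is open, and one sentence would close it. The section heading is weak evidence of a narrow scope, because the whole-cohort sentence stands under the same heading. Keeping eligible patients in results that do not need SOFA also respects the consecutive design.

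Much of this stands: the scope is not stated, and stating it would be cheap. What does not follow is that the results are at risk. Nor is one remedy plainly better. Limiting the exclusion keeps more patients, but the overall total then exceeds the sum of the tertiles and needs a footnote. Defining the analysed cohort as patients with at least one baseline component makes the columns add up, at the cost of a few patients. Reasonable statisticians could choose either.

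**Conclusion.** No change follows. The SAP leaves the scope of one exclusion unstated, which is a gap that analysts can fill sensibly; it does not contradict itself. Under either reading the tertile comparisons and the Cox model use the same patients, and the overall results should differ by very little: about 5 to 10 mL if 1% of patients have no SOFA component and their mean volume differs by 500 to 1000 mL. The true effect cannot be computed from the SAP, because it does not give that share.

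The conclusion rests on the share being small. The rule that one component suffices and the daily data collection make this likely. It will also be open to inspection: the planned participant flow diagram (eFigure 1) and the table of missing data by variable should show how many patients had no baseline SOFA. An unexpectedly large number would be visible to the reader.

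### Does the 166 mL/h line leave resuscitation volume undefined for slower fluid given for hemodynamic impairment?

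*SAP*

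**What the plan says.** The Primary outcome section of the SAP takes fluid volume by indication over the first 3 days of invasive ventilation, with emphasis on resuscitation fluid. The Analysis plan then describes the indication categories.

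- **Resuscitation:** the reason is "Prescribed in response to hemodynamic impairment or shock" and the rate is "At a rate of at least 166ml/h (1L/6 hours". Two further lines, on fluid type and on speed ("Usually much faster or as a bolus"), are softened by the word usually. The rate line is not.
- **Maintenance:** covers daily needs, and its rate line reads "Up to 100 ml/h infusion rate".
- **Replacement:** the reason line reads "To address fluid losses". The rate line is permissive, "Can have faster (e.g. > 100ml/h) infusion rates", and a separate line on mode of delivery rules out a bolus.
- **Unknown:** a remaining category takes whatever cannot be sorted, worded as "Prescribed intravenous fluid therapy for which it is impossible to distinguish between resuscitation, maintenance or replacement".

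The SAP does not say whether every line under a category must be met, or which line prevails when two disagree.

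**The concern.** Fluid given for hemodynamic impairment below 166 mL/h has the resuscitation reason but not the resuscitation rate. It may fit the maintenance or replacement rate lines, but it has neither of their reasons. Nor is it plainly of unknown indication, since the reason is known. A bolus given for losses without hemodynamic impairment raises a similar question: it has the replacement reason, is barred from replacement by its mode of delivery, and lacks the resuscitation reason.

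The sorting rule defines the primary outcome, so the same infusion could count in full or not at all. Category volumes are also reported as percentages of the total. If some fluid belonged to no category, the indication categories would not add up to all prescribed intravenous fluid. The supplementary table of mean volumes per indication shows results only after sorting, so it would not reveal how such cases were handled.

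**Working it through.** **Inputs, all from the SAP's Analysis plan:** resuscitation floor 166 mL/h, stated as 1 L in 6 hours; maintenance limit 100 mL/h; replacement may exceed 100 mL/h, with no upper limit given.

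**1. The stated figure.** 1,000 mL / 6 h = 166.67 mL/h, and 166 × 6 = 996 mL. The 166 is this value truncated, so the line agrees with itself.

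**2. Where the lines disagree, for fluid with a hemodynamic reason.**

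| Rate (mL/h) | Resuscitation reason | Resuscitation rate | Other rate lines that admit it |
|---|---|---|---|
| 100 or less | met | not met | maintenance, replacement |
| above 100, below 166 | met | not met | replacement only |
| 166 or more | met | met | no conflict within resuscitation |

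**3. A worked case.** 1,000 mL / 8 h = 125 mL/h, and 100 < 125 < 166. For this litre, in mL:

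| Reading | Resuscitation | Maintenance or replacement | Unknown | No category |
|---|---|---|---|---|
| Reason decides | 1,000 | 0 | 0 | 0 |
| Both required, remainder to Unknown | 0 | 0 | 1,000 | 0 |
| Both required, remainder unplaced | 0 | 0 | 0 | 1,000 |
| Rate decides | 0 | 1,000 | 0 | 0 |

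**4. How well the text supports each reading.**

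- *Reason decides.* The SAP calls the groups indication categories, and an indication is a reason. The rate line then describes typical delivery.
- *Both required.* Unqualified lines are criteria, and lines with usually are description. Slow fluid is then simply not resuscitation, and resuscitation volume is determinate. Only the destination of the remainder is open. The Unknown wording concerns fluid that cannot be told apart between categories, so fluid with one category's reason and another's rate can fairly go there, although the category's name leans towards an unknown reason. The unplaced row is therefore not forced, and the percentages can still add up.
- *Rate decides.* This has little support. The replacement rate line is permissive and does not draw in fluid given for another reason. Sorting by rate alone would also take a 200 mL/h non-bolus infusion for burns out of replacement, although the SAP names burns as an example of replacement.

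On the quantities the SAP plans to report, the example moves at most 1,000 mL into or out of any one category.

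**5. Size in a patient.** Let V be the volume given for hemodynamic reasons and s the share of it given below 166 mL/h. Resuscitation volume is V if the reason decides and V(1 − s) if both lines are required. The SAP gives neither quantity. Assuming V = 2,000 mL:

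| s (assumed) | Reason decides (mL) | Both required (mL) |
|---|---|---|
| 0% | 2,000 | 2,000 |
| 10% | 2,000 | 1,800 |
| 20% | 2,000 | 1,600 |
| 30% | 2,000 | 1,400 |
| 50% | 2,000 | 1,000 |

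The floor gives no per-patient maximum. One infusion just below it delivers under 166 × 24 = 3,984 mL per day, but infusions can run concurrently.

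**The case for a change.** The strongest case for a change is that this is the primary outcome, that at least 200 ICUs in 30 countries are expected to contribute, and that one sentence would settle which line prevails. If sites apply these definitions themselves, different readings could enter the data unseen. If the reason decides, the unqualified floor has no effect, which is an odd way to write a criterion. It is also no full answer that the protocol or case report form may settle the matter, because the SAP states definitions of its own.

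Part of this stands: the wording is open, and the floor's role is not stated. The rest is weaker. The Design section has fluid data collected daily for the previous day, and results are planned by indication and study day. That suggests the indication is recorded at collection, although the SAP does not say so. In that case a sentence in the SAP would not alter how sites classified fluid, and the analyst would use the recorded category. If the analyst does have to sort, asking the SAP to say which line decides identifies no better rule than either natural reading.

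A sensitivity analysis that reallocates Unknown volume would not close the gap either. It reaches only the slow fluid that was placed in Unknown, not fluid kept in resuscitation, counted as maintenance or replacement, or left out.

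The bolus for losses is a minor case. Its exclusion from replacement is explicit, only its destination is open, and nothing in the SAP suggests a material volume.

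**Conclusion.** No change to the plan follows. The SAP leaves open where fluid meeting only the resuscitation reason is counted, but this is a gap that data collectors and analysts can fill sensibly. Letting the reason decide, or requiring both lines and placing the remainder in Unknown, gives a coherent resuscitation volume that can be applied alike in every SOFA tertile.

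The choice is worth 1,000 mL per litre of such fluid within the resuscitation category. The total affected, and any effect on the tertile comparison, cannot be shown in size or direction, because the SAP gives no share of hemodynamically indicated fluid run below 166 mL/h. That share could differ between tertiles, so an effect is not excluded.

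The conclusion rests on two assumptions: that the indication is assigned when data are collected or, failing that, that one reading is used throughout; and that the affected volume is modest, as the SAP's own description of resuscitation delivery suggests. No view is taken on which rate is right.

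### The primary mean volumes get 95% CIs, but no CI or volume model accounts for ICU; patient-level CIs would be too narrow if the means are to speak beyond the participating ICUs

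*SAP*

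**What the plan says.** The Design section describes a clustered sample: "We expect a minimum of 200 ICUs from 30 countries to participate in this study", and "Centers are expected to include 20 consecutive patients", with optional further blocks of 20.

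The primary outcome is fluid volume per indication over the first 3 days, chiefly resuscitation fluid. The Analysis plan sets its precision measure: "These volumes will be described as absolute mean volumes in mL with 95% confidence interval", and the same per kilogram of body weight. The Stratification section states "Outcomes will be analyzed across the entire cohort" and then adds SOFA tertiles. In the list of tables and figures, one eTable 2 is described as "Mean volumes per indication for fluid administration per study day and stratification variable".

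The volume regression compares SOFA tertiles and looks for influences on fluid management, "adjusting the administered fluid volumes for the following baseline variables: duration of first study day; sex; age; weight; and admission diagnosis". Its results appear to feed eTable 4, on factors associated with fluid management.

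The SAP nowhere mentions an ICU or country term, a random effect, a clustered variance or a cluster bootstrap. Two clauses are left open. One allows further covariates, but it follows the Cox model. The other reads "Sensitivity testing will be performed to assess the robustness of findings" and names no analysis.

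**The concern.** Patients in one ICU share prescribers, local protocols and case mix, so their fluid volumes may be correlated. A CI computed as if all patients were independent ignores that source of variation. The SAP does not tell the analyst to allow for it, and the simplest CI for a mean would comply fully with the text.

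The 95% CI is the only measure of uncertainty specified for the primary mean volumes. If readers take those means as practice in ICUs generally, an interval labelled 95% may cover much less often than that. The volume regression has a related weakness: a covariate that itself varies between ICUs, such as admission diagnosis, can get a standard error that is too small.

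**Working it through.** There is no figure in the plan to reproduce: the SAP gives no total sample size, SD or ICC.

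**Inputs from the SAP:** 200 ICUs (minimum), 20 patients per ICU (expected intake), 30 countries, three SOFA tertiles.

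**Assumed:** ICC of 0.01, 0.05, 0.10 and 0.20; tertiles spread evenly, so 20/3 = 6.67 patients per ICU and tertile. A case with 10 per ICU (3.33 per tertile) stands for centres that do not reach 20. The total of 200 × 20 = 4,000 is illustrative.

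**Formulas**, for inference beyond the participating ICUs:
- design effect DE = 1 + (m − 1) × ICC, with m patients per ICU;
- CI width factor = √DE;
- coverage of a nominal 95% patient-level CI = 2Φ(1.96/√DE) − 1.

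Example: m = 20, ICC = 0.05 gives DE = 1 + 19 × 0.05 = 1.95, √1.95 = 1.40, and coverage 2Φ(1.96/1.40) − 1 = 84.0%.

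| Means | ICC 0.01 | 0.05 | 0.10 | 0.20 |
|---|---|---|---|---|
| Whole cohort, m = 20: DE | 1.19 | 1.95 | 2.90 | 4.80 |
| – width factor | 1.09 | 1.40 | 1.70 | 2.19 |
| – coverage | 92.8% | 84.0% | 75.0% | 62.9% |
| Per tertile, m = 6.67: DE | 1.06 | 1.28 | 1.57 | 2.13 |
| – width factor | 1.03 | 1.13 | 1.25 | 1.46 |
| – coverage | 94.3% | 91.6% | 88.3% | 82.0% |
| Whole cohort, m = 10: coverage | 94.0% | 89.6% | 84.5% | 75.9% |
| Per tertile, m = 3.33: coverage | 94.7% | 93.6% | 92.2% | 89.4% |

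**Absolute width.** Half-width = 1.96 × √(DE/n) in SD units. At n = 4,000 it is 0.034/0.043/0.053/0.068 SD instead of 0.031. At n = 1,333 (one tertile) it is 0.055/0.061/0.067/0.078 SD instead of 0.054.

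**Unequal ICU sizes.** With DE = 1 + ((cv² + 1) × m − 1) × ICC and an assumed coefficient of variation of 0.7, ICC 0.05 gives DE = 1 + (1.49 × 20 − 1) × 0.05 = 2.44 and coverage 79%.

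**If the participating ICUs are the whole target.** The ICUs then act as fixed strata, the variance of the mean is (1 − ICC) × SD²/n, and the patient-level CI covers 95.1/95.6/96.1/97.2%. There is no problem.

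**Simulation check on skewed volumes** (lognormal, log-SD 1, 200 ICUs of 20, 2,000 runs per cell). Patient-level coverage was 93.2/84.8/76.6/62.4% for the whole cohort and 93.4/90.3/87.4/79.2% per tertile. ICU-clustered CIs gave 94.2–95.6% and 93.4–94.4%.

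**Volume regression** (simulated with normal volumes, tertile indicators and one binary diagnosis of 25% prevalence; SOFA ICC 0.10 assumed). With patient-level standard errors, the type I error for the diagnosis coefficient, over assumed diagnosis ICCs of 0.05–0.20, was about 5% at fluid ICC 0.01, 5–6% at 0.05, 6–10% at 0.10 and 7–13% at 0.20. For highest versus lowest tertile it was 4–8%. ICU-clustered errors gave about 4–6% for both. A separate simulation without the diagnosis term gave 93–95% coverage for the tertile difference with patient-level errors.

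**Country.** ICU clustering does not capture correlation between ICUs of one country. With 200/30 = 6.67 ICUs per country, the true DE is 1.95 + 5.67 × 20 × ρ at ICU ICC 0.05, where ρ is the assumed correlation between patients in different ICUs of one country. At ρ = 0.01/0.02/0.05 this is 3.08/4.22/7.62. An ICU-clustered CI, which reflects a DE of about 1.95, then covers about 88/82/68% for inference beyond the participating countries.

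**The case against.** The strongest reply is that the SAP is silent rather than wrong. It names no CI method, so ICU-clustered intervals would comply with it, and a reader who infers that it prescribes patient-level CIs goes beyond the text. That stands. But choosing the variance for a primary CI belongs in the analysis plan, and this one describes clusters, requires intervals and leaves the choice open.

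It also stands that the harm needs a target wider than the participating ICUs and a material ICC, and that the SAP states neither. At ICC 0.01 the per-tertile loss is negligible.

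The consequence is limited. The volumes are described rather than tested against a threshold, and the intervals stay narrow in absolute terms. The lowest coverages concern whole-cohort means, whereas the listed volume displays are by stratification variable. Whole-cohort analysis is nevertheless planned in the text.

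Three stronger readings are tempting and unsupported:
- That comparisons between SOFA tertiles are invalid. Tertiles vary within ICU, and these contrasts are little affected.
- That Figure 2, "A three panels figure of line plots with 95% CI showing" fluid input, output and balance, carries the primary result. It covers totals over 7 days, not volume per indication over 3 days.
- That clustering by ICU guarantees 95% coverage. The simulations drew ICUs independently at random; the SAP describes no random sampling of ICUs, and correlation within country would remain.

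**Conclusion.** The point holds in conditional form. No CI and no volume model in the SAP accounts for ICU, and the target of inference is not stated. If the means are to describe practice beyond the participating ICUs, patient-level CIs overstate precision whenever volumes correlate within ICU. The loss is moderate to large for whole-cohort means, smaller per tertile, and smaller again for most regression coefficients. Only covariates that vary between ICUs, such as admission diagnosis, show a noticeable effect in the regression.

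The absence of any ICU term is certain. The size of the effect is not: every magnitude rests on an assumed ICC. The fault lies in the stated uncertainty alone; a reader should not infer that the estimated volumes are biased. It is worth correcting because the remedy is cheap and uses data already held.

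**What to change.** - State whether the mean volumes describe the participating ICUs only or practice beyond them. If only the former, that one sentence settles the matter for the means.
- If the target is wider, state that the 95% CIs for mean volumes per indication (mL and mL/kg, whole cohort and per tertile, including the eTable 2 on volumes) use cluster-robust or cluster-bootstrap variance with ICU as the cluster. Add a sensitivity analysis that clusters by country.
- In the volume regression, use ICU-clustered standard errors or a random ICU intercept, mainly for the sake of the covariate results in eTable 4.
- Report the ICC for resuscitation volume.
- The 7-day CIs in Figure 2 can follow the same method for consistency. ICU-clustered variance in the Cox model is optional, and no change to the Kruskal-Wallis test is needed.

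The cost is a few sentences and slightly more code, since the enrolling ICU is known for every patient. The downside is wider intervals: at 20 per ICU, by a factor of 1.09 to 2.19 for the whole cohort and 1.03 to 1.46 per tertile over the assumed ICCs. If the ICC proves negligible, they barely change.
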